17.4.4. Intravenous Fibrinolytics

Examples of fibrinolytics include the following:

- Tissue plasminogen activator (tPA, alteplase, Activase®),
- TNK (tenecteplase, TNKase®),
- rPA (reteplase, Retavase®),
- Streptokinase (Streptase®),
- Anistreplase (Eminase®).

If a subject requires treatment with a fibrinolytic agent, then study drug must be discontinued.

17.4.5. NSAIDs (excluding aspirin)

While on study drug, NSAIDs cannot be taken for >4 days per week. Less frequent use of NSAIDs is permitted while on study drug. However, the Investigator should weigh the

benefit/risk of NSAID use in combination with an oral anticoagulant for the individual subject. Examples of NSAIDs include the following:

Aceclofenac	Acemetacin	Alclofinac
Amtolmetin	Axapropazone	Benoxyprofen
Bromfenac	Bufexamac	Carprofen
Clonixin	Dexibuprofen	Dexketoprofen
Diclofenac	Diclofenac/Hyaluronic Acid	Diflunisal
Dipyrrone	Droxicam	Etodolac
Etofenamate	Felbinac	Felbufen
Fenoprofen	Fentiazac	Floctafenine
Flufenamic Acid	Flurbiprofen or fluribuprofen	Hydrocodone/Ibuprofen
Ibuprofen	Indomethacin	Indoprofen
Ioxicam	Ketoprofen	Ketorolac
Lansoprazole/Naproxen	Lornoxicam	Loxoprofen
Meclofenamate	Mefanamic Acid	Meloxicam
Morniflumate	Nabumetone	Naproxen
Niflumic Acid	Nimesulide	Oxaprozin
Oxycodone/Ibuprofen	Phenylbutazone	Piketoprofen
Pirazolac	Piroxicam	Piroprofen
Prophenazone	Proquazone	Sulindac
Suprofen	Tenidap	Tenoxicam
Tiaprofenac acid	Tolmetin	Zomepirac

17.4.6. P-gp Inhibitors List (Not Prohibited Medication but Requires Dose Adjustment)

Use of P-gp inhibitors during the treatment with edoxaban will require dose reduction either at randomization or during the course of the study. The only exemption from this rule is the use of amiodarone which will not require dose reduction.

Below are examples (but not limited to) the most commonly used P-gp inhibitors:

Table 17.5: P-gp Inhibitors List

Drug Class	Drug Name
Antiarrhythmics	Amiodarone, quinidine, verapamil, dronedarone, carvedilol, ranolazine
Antibiotics	Clarithromycin
Anti-fungal	Itraconazole
Others	Lapatinib, lopinavir, ritonavir, propafenone, saquinavir, telaprevir, and tipranavir

17.4.7. P-gp Inducers List (Prohibited Medication)

Rifampin is a P-gp inducer that has been shown to lower the edoxaban exposure. The example medications listed below (but not limited to) have not been tested with edoxaban but are also P-

gp inducers. These should be avoided during the study as their use may lead to a lower exposure of edoxaban than predicted for clinical efficacy. (<http://www.straighthealthcare.com/p-glycoprotein.html#inducers>)

- Rifampin
- Carbamazepine (Tegretol®)

17.5. Transition from Edoxaban to Other Anticoagulants

Subjects who require anticoagulation at the end of study participation will be transitioned to standard-of-care treatment as directed by the Investigator or treating physician.

At the end of edoxaban treatment, the subject will receive the last dose of edoxaban and all remaining edoxaban tablets/bottles will be collected from the subject by site staff.

When transitioning from edoxaban to VKA:

Subjects transitioning to any VKA from edoxaban will have their INR recorded at last study visit. Bridging with heparin may occur during VKA titration until the INR is at therapeutic level of between 2.0 and 3.0.

INR will need to be measured as frequently as necessary until the INR target of ≥ 2.0 . Once the INR is ≥ 2.0 the heparin will be stopped and the subject will continue on the VKA alone.

When transitioning from edoxaban to another direct oral anticoagulant (eg rivaroxaban, apixaban, dabigatran):

- The first dose of the direct oral anticoagulant of choice will be given 24 hours post the last dose of edoxaban and will then be continued as per the novel anticoagulant's label.

For subjects who do not complete the Main Treatment Period, they will be followed with monthly visits until the end of Month 3 plus a Follow-Up Visit according to the Schedule of Events ([Table 17.1](#)).

For subjects who completed the Main Treatment Period but do not continue into the Extension Treatment Period, a Follow-Up Visit (9) will occur 30 days after the Month 3 visit.

For subjects who continue into the Extension Period, the Follow-Up Visit will occur 30 days after the Discontinuation Visit.

17.6. Management of Serious/Life-Threatening Bleeding

The following steps are currently recommended²⁶ for subjects with ongoing major bleeding (see Section [9.2.1](#)):

- Withhold study drug and all antiplatelets / anticoagulants
- Institute SOC for major bleeding (large bore IV or central venous line, type and crossmatch blood, admit to the intensive care unit, provide hemodynamic and respiratory support)
- Administer packed red blood cells (or whole blood) as needed

- Administer antidotes if applicable

For LMWH:

The antidote for LMWH is protamine sulphate.

The dose of protamine sulphate given is dependent upon the dose of LMWH administered and the time of administration.

Suggestions from the Sponsor:

If protamine is given within 8 hours of the LMWH then a maximum neutralizing dose is 1 mg protamine/100 units (or 1 mg) of LMWH given in the last dose.

If more than 8 hours have passed since the dose of LMWH was given, administer 0.5 mg protamine per 1 mg (100 units) of LMWH given.

Protamine is administered by slow IV infusion (over 10 minutes) to avoid a hypotensive reaction.

Protamine is a medication that requires a high level of caution when being prescribed and administered. Outside cardiac surgery and ICU, consultant or fellow approval is required for the use of protamine- do not allow this to lead to delayed administration in the case of bleeding. Contact the appropriate senior person immediately.

For Warfarin:

Significant but not life-threatening bleeding: Administer Vitamin K 0.5 mg to 2 mg SC (NOT intramuscularly) plus FFP (20 mL/kg IV) to a maximum of 4 units.

Major bleeding (any INR) or requiring emergency surgery doses if INR >8

- Stop warfarin
- Vitamin K (30 µg/kg) IV, consider higher doses if INR >8
- Prothrombin complex concentrate (PCC) replacement therapy (NB FFP gives inferior correction and is not recommended):
 - Beriplex® [4-factor Prothrombin Complex Concentrate approved in several EU countries] (and Kcentra® approved in the US) (Discuss with on call haematologist)
 - Beriplex dosage is calculated based on the current INR and subject's weight (see table below)
 - Repeat the INR following PCC
 - Further doses of Beriplex or Vitamin K may be required

INR	Approximate Dose
2.0-3.9	1 mL/kg = 25 IU/kg
4.0-6.0	1.4 mL/kg = 35 IU/kg
>6.0	2 mL/kg = 50 IU/kg

For Edoxaban:

Although not evaluated in clinical trials, PCC, activated prothrombin complex concentrates (aPCCs), or recombinant Factor VIIa could be considered for the reversal of the anticoagulant effect of edoxaban. In healthy volunteers, a 3-factor PCC restored thrombin generation (AUC for thrombin generation curve) but did not normalize PT. Thus, a 3-factor PCC may be of some value in reversing anticoagulant effects of edoxaban (Study A-U150).

A specific reversal agent for edoxaban is not available. Although not evaluated in subjects, PCC (Beriplex® or Kcentra®), aPCCs, or recombinant Factor VIIa could be considered for the reversal of the anticoagulant effect of edoxaban.

The following are not expected to reverse the anticoagulant effects of edoxaban:

- protamine sulfate,
- vitamin K,
- tranexamic acid.

Hemodialysis does not significantly contribute to edoxaban clearance.

In the event of a Medical Emergency, the Investigator at the study site will institute any medical procedures deemed appropriate. A 24-hour Urgent Medical Contact will be provided to contact the Medical Monitor for further guidance.

Sites will receive a contact card where the following numbers (24-hour Urgent Medical Contact) are provided:

PPD [REDACTED] (primary number)

PPD [REDACTED] (alternative number)

The medical call center will contact Medical Monitor for the assigned region.

17.7. Estimated Glomerular Filtration Rate (eGFR) Assessment

Age (Sex)	Normal eGFR (Mean eGFR±SD) (mL/min/1.73 m ²)	30% eGFR for Study Qualification ^a (Mean eGFR) (mL/min/1.73 m ²)	eGFR Threshold for Dose reduction ^b (Mean eGFR) (mL/min/1.73 m ²)
1 week (males and females)	41 ± 15	10	15
2-8 weeks (males and females)	66 ± 25	10	20
>8 weeks (males and females)	96 ± 22	20	35
2-12 years (males and females)	133 ± 27	30	50
13-21 years (males)	140 ± 30	35	55
13-21 years (females)	126 ± 22	30	50

eGFR: estimated glomerular filtration rate; m: meters; min: minutes; mL: milliliter; SD: standard deviation
Ref: American Journal of Kidney Diseases, Vol 39, No 2, Suppl 1 (February), 2002: pp S46-S75

^a may be enrolled if eGFR is at or greater to this value as determined by the age appropriate formula indicated below:

^b eGFR must be less than this value for dose reduction (which corresponds to approximately ≤50% eGFR).

Modified Schwartz equation (pediatric subjects <12 years of age):

$$\text{CrCl (mL/min/1.73 m}^2\text{)} = (\text{K} * \text{Ht}) / \text{Scr}$$

height (Ht) in cm; serum creatinine (Scr) in mg/dL

K (proportionality constant): 656

Infant (LBW <1 year): K=0.33

Infant (Term <1 year): K=0.45

Female Child (<12 years): K=0.55

Male Child (<12 years): K=0.70

Cockcroft-Gault equation (pediatric subjects ≥12 years of age):

$$\text{CrCL (mL/min)} = [(\text{140} - \text{age}) \times \text{weight in kg}] / [\text{Scr} \times 72] (\times 0.85 \text{ if female})$$

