- The edoxaban dosage regimen will be reduced permanently for subjects with moderate renal impairment (eGFR) $\geq 30\%$ to $\leq 50\%$ of normal for the subject's age and size at randomization as determined by the age-appropriate formula: Cockcroft-Gault equation for pediatric subjects ≥ 12 years of age and modified Schwartz equation for pediatric subjects <12 years of age (Appendix 17.7). If a subject experiences a change in renal function from normal to eGFR $\geq 30\%$ to $\leq 50\%$ after randomization, the measurement will be repeated within 1 week to 10 days after correction of the underlying factor's causing pre-azotemia. If the repeat measurement confirms the reduced eGFR, the edoxaban dose will be reduced permanently.

- Additionally, if a subject requires concomitant administration of a certain P-glycoprotein (P-gp) inhibitor (Appendix 17.4.6), the edoxaban dose will be reduced during P-gp administration and re-established to the original dose once P-gp inhibitor administration had concluded.
- Subject is ≤ 28 days old (corrected for gestation age of 38 weeks). This may change based on the IDMC recommendation.

Randomization to Standard of Care Treatment Arm

Standard of care treatment will be dispensed to the subject on a monthly visit schedule. After Month 3, on a case-by-case basis, confirmed by the Sponsor, a 3-month dispense may occur to facilitate subject travel arrangements.

Local SOC sourcing:

The SOC will be provided by the Investigator. Subject will be treated with LMWH, VKA, or SP Xa inhibitors according to the site SOC treatment regimen (see Section 5.1.1.2).

Central/Sponsor Sourcing:

However, if there are regulatory or site hurdles providing the SOC, the Sponsor will provide SOC as enoxaparin or fondaparinux or warfarin as follows:

- Enoxaparin – Subjects will be treated with enoxaparin alone or can be switched to warfarin anytime during the study treatment period.
 - Enoxaparin (LMWH) will be provided to the subjects as solution for subcutaneous (SC) injection in pre-filled syringes with 60 mg/0.6 mL, 80 mg/0.8 mL, and 100 mg/1.0 mL concentration for injection, or as multiple dose vials (for subjects < 10 kg) for injection where allowed per standard clinical practice.
- Fondaparinux – Subjects will be treated with fondaparinux alone or can be switched to warfarin anytime during the study treatment period.

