4.2. Exclusion Criteria

Subjects who meet any of the following criteria will be disqualified from entering the study:

1. Subjects with active bleeding or high risk of bleeding contraindicating treatment with LMWH, SP Xa inhibitors, VKAs, or direct oral anticoagulants (DOACs; identified high risk of bleeding during prior experimental administration of DOACs).
2. Subjects who have been or are being treated with thrombolytic agents, thrombectomy or insertion of a caval filter for the newly identified index VTE.
3. Administration of antiplatelet therapy is contraindicated in both arms except for low dose aspirin defined as 1-5 mg/kg/day with maximum of 100 mg/day (see Appendix [17.4.1](#)).
4. Administration of rifampin is prohibited during the study and subjects on concomitant use of rifampin are excluded.
5. a) Subjects with severe hepatic impairment or hepatic disease associated with coagulopathy (eg, acute hepatitis, chronic active hepatitis, and cirrhosis).

- b) Subjects with ALT $>5 \times$ the upper limit of normal (ULN) or total bilirubin $>2 \times$ ULN with direct bilirubin $>20\%$ of the total at Screening.
- c) Subjects with aPTT >50 seconds or international normalized ratio [INR] >2.0 not related to anticoagulation therapy).
- 6. Subjects with estimated glomerular filtration rate (eGFR) $<30\%$ of normal for age and size (see Appendix 17.7).
- 7. Subjects with stage 2 hypertension defined as blood pressure (BP) systolic and/or diastolic confirmed $>99^{\text{th}}$ percentile + 5 mmHg (see Appendix 17.8).
- 8. Subject with thrombocytopenia $<50 \times 10^9/\text{L}$ at Screening Visit. Subjects with a history of heparin-induced thrombocytopenia may be enrolled in the study at the Investigator's discretion.
- 9. Life expectancy less than the expected study treatment duration (3 months).
- 10. Subjects who are known to be pregnant or breastfeeding.
- 11. Subjects with any condition that, as judged by the Investigator, would place the subject at increased risk of harm if he/she participated in the study including contraindicated medications identified in Appendix 17.4.
- 12. Subjects who participated in another interventional clinical study or were treated with an experimental therapy with less than a 30 day wash-out period prior to identifying the qualifying index VTE.
- 13. Hypersensitivity to the active ingredient or to any of the excipients of any components of the trial treatment.

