5.1.1.1.1. Edoxaban dose recommended for 12 to <18 years old pediatric subjects

Edoxaban treatment will be dispensed to the subject on a monthly visit schedule (see caveat above). The oldest cohort (12 to <18 years old) will receive tablets (15 and/or 30 mg strength, see [Table 5.1](#)). (Doses for all subsequent age cohorts will be by notification to the investigative sites.) Subjects will be instructed to take edoxaban (tablets) orally once a day, at the same time every day, with or without food. Tablets should be swallowed with a glass of water.

Only on Day 5 (+3), the approximately first 12 subjects participating in PK/PD assessment should be fasting one hour prior to intake of edoxaban dose and a maximum of 2 hours after taking edoxaban dose.

Table 5.1: Edoxaban Dose Recommended For All 5 Cohorts (12 to <18 years, 6 to <12 years, 2 to <6 years, 6 months to <2 years, and birth to <6 months)

Age	Body Weight	Dose (Tablet)	Dose (Suspension) (6 mg/mL concentration) ^{c,e}	Dose Reduction ^a
12 to <18 years ^b (At date of consent)	≥60 kg	60 mg QD	NA	45 mg QD
	≥30 and <60 kg	45 mg QD	NA	30 mg QD
	<5th Percentile for Age ^c	30 mg QD	NA	NA
6 to <12 years (At date of consent)	<60 kg Dosed based on mg/kg ^d	NA	1.2 mg/kg with a maximum dose of 45 mg	0.8 mg/kg, with a maximum dose of 45 mg
2 to <6 years (At date of consent)	Dosed based on mg/kg	NA	1.4 mg/kg with a maximum dose of 45 mg	0.7 mg/kg, with a maximum dose of 24 mg
6 months to <2 years (At date of consent)	Dosed based on mg/kg	NA	1.5 mg/kg with a maximum dose of 45 mg	0.75 mg/kg with a maximum dose of 24 mg
>28 days to <6 months (At date of consent)	Dosed based on mg/kg	NA	0.8 mg/kg with a maximum dose of 12 mg/kg	0.4 mg/kg, with a maximum dose of 6 mg/kg
38 weeks gestation to ≤28 days (At date of consent)	Dosed based on mg/kg	NA	To be determined by the IDMC	0.4 ^f mg/kg, with a maximum dose of 6 mg/kg

Abbreviations: eGFR = estimated glomerular filtration rate; IDMC = Independent Data Monitoring Committee; NA = not applicable; P-gp = P-glycoprotein; QD = once a day

^a Conditions for dose reduction:

If a subject requires concomitant administration of P-gp inhibitor (Appendix 17.4.6), the edoxaban dose will be reduced during P-gp administration and re-established to the original dose once P-gp inhibitor administration had concluded.

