Edoxaban dosage regimen will be reduced permanently for subjects with moderate renal impairment for the subject's age and size at randomization as determined by the age appropriate formula: Cockcroft-Gault equation for pediatric subjects ≥12 years of age and modified Schwartz equation for pediatric subjects <12 years of age). Refer to Appendix 17.7 for eGFR values below which dose reduction should be implemented.

If a subject experiences a change in renal function from normal to eGFR ≥30% to ≤50% after randomization, the measurement will be repeated within 1 week to 10 days after correction of the underlying factor's causing pre-azotemia. If the repeat measurement confirms the reduced eGFR, the edoxaban dose reduction will be permanent even if the subject experiences an improvement in the eGFR during the course of the study.

^b Dose reduction due to body weight applies only for fixed doses in subjects 12 to <18 years of age:

If body weight increases or decreases from the categories of weight defined at consent, the subject will be dose adjusted. Subjects who are ≥60 kg of body weight at consent and drop below that body weight will receive 45 mg dose at any subsequent visit. Subjects who are ≥30 and <60 kg at consent and increase their weight to ≥60 kg will increase their dose to 60 mg.

^c Edoxaban dosage regimen will be reduced permanently for subject with body weight <5th percentile for age.
Refer to Appendix 17.9.

^d Edoxaban granulation will be diluted with 8 mL water to provide a concentration of 6 mg/mL dosing suspension. If body weight increases or decreases from the categories of weight defined at consent, the subject will be dose adjusted. Subjects who are \geq 60 kg of body weight at consent and drop below that body weight will receive 45 mg dose at any subsequent visit. Subjects \geq 30 and <60 kg at consent increasing their weight to \geq 60 kg will increase their dose to 60 mg.

Note: Dose is based upon weight at corresponding visit.

^e Edoxaban granules are for subjects <12 years of age only. Subjects 12 to <18 years of age should use crushed edoxaban tablets. For those subjects cannot swallow whole tablets, edoxaban tablets may be crushed and mixed with 2 to 3 ounces of water and immediately administered by mouth or through a gastric tube. The crushed tablets may also be mixed into applesauce and immediately administered..

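### For ages 12 to <18, Appendix 17.7 compares a Cockcroft-Gault result in mL/min with eligibility and dose-reduction cut-offs in mL/min/1.73 m², with no conversion for body surface area

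*Combined protocol and SAP*

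**What the plan says.** The table in Appendix 17.7 has three value columns: normal eGFR, the cut-off for study qualification and the threshold for dose reduction. All three are headed mL/min/1.73 m². Footnote a says a subject "may be enrolled if eGFR is at or greater to this value as determined by the age appropriate formula indicated below". Footnote b says "eGFR must be less than this value for dose reduction (which corresponds to approximately" half of normal.

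Two formulas follow. Modified Schwartz, for children under 12, is printed with its result in mL/min/1.73 m². The other is headed "Cockcroft-Gault equation (pediatric subjects ≥12 years of age"). Its result is printed in mL/min, and it contains weight but no height or BSA term. The Synopsis repeats the assignment, with renal function "as determined by the age-appropriate formula: Cockcroft-Gault equation for pediatric subjects" of 12 and over.

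The table is operative. Exclusion 6 (Section 4.2) refers to it. So do the IXRS dose-reduction entry (Section 5.1.2) and the dose-reduction rule (Section 5.3.1). Footnote a of Table 5.1 says "Refer to Appendix 17.7 for eGFR values below which dose reduction should be implemented". Section 9.8.3, on how eGFR is obtained, only points back to the same appendix.

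**The concern.** The formula result and the cut-off are in different units for one age cohort only. Under 12 years, both are per 1.73 m². From 12 to <18, an absolute clearance is read against an indexed threshold. The two agree only when BSA is 1.73 m², and this cohort spans a wide range of body sizes.

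Two decisions depend on the comparison. Eligibility is affected before randomization, so in both arms. Dose is affected in the edoxaban arm only: Table 5.1 reduces 60 mg to 45 mg at 60 kg and above, and 45 mg to 30 mg from 30 to <60 kg. Renal dose reduction is meant to last. After a confirmed fall in eGFR, "the edoxaban dose reduction will be permanent even if the subject experiences an improvement in the eGFR". In a large adolescent the risk is a full anticoagulant dose at a renal function below the tabled threshold. In a smaller one it is needless exclusion or lasting under-dosing.

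**Working it through.** **Inputs from Appendix 17.7.** Qualification / dose-reduction cut-offs, in mL/min/1.73 m²: males 13-21 years, 35 / 55; females 13-21 years, 30 / 50; 2-12 years, 30 / 50. A 12-year-old uses Cockcroft-Gault but falls in the 2-12 years row.

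Cockcroft-Gault (CG) = (140 − age) × kg / (72 × Scr), × 0.85 if female, in mL/min.

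**Assumptions, not in the protocol.** BSA = √(kg × cm / 3600) (Mosteller). All body sizes and creatinine values below are mine.

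**Step 1: effective cut-off.** The indexed result is CG × 1.73/BSA. Testing CG < T is therefore the same as testing the indexed result against T × 1.73/BSA.

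| Tabled cut-off | BSA 1.3 | BSA 1.9 | BSA 2.1 |
|---|---|---|---|
| Reduction 55 (males 13+) | 73.2 | 50.1 | 45.3 |
| Reduction 50 (females 13+; age 12) | 66.5 | 45.5 | 41.2 |
| Qualification 35 (males 13+) | 46.6 | 31.9 | 28.8 |
| Qualification 30 (females 13+; age 12) | 39.9 | 27.3 | 24.7 |

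For example, 55 × 1.73 / 1.3 = 73.2. The factor 1.73/BSA is 1.60 at 30 kg and 140 cm, 1.03 at 60 kg and 170 cm, and 0.74 at 110 kg and 180 cm.

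**Step 2: a large adolescent.** Girl of 16, 95 kg, 165 cm.
- BSA = √(95 × 165 / 3600) = 2.087.
- CG = 124 × 95 × 0.85 / (72 × Scr) = 139.07/Scr.
- Indexed = 139.07 × 1.73 / 2.087 / Scr = 115.3/Scr.
- Reduction at 50: unindexed above Scr 139.07/50 = 2.78 mg/dL; indexed above 115.3/50 = 2.31.
- Exclusion at 30: unindexed above 139.07/30 = 4.64; indexed above 115.3/30 = 3.84.

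Between 2.31 and 2.78 mg/dL she stays on 60 mg when the tabled threshold, read in its own units, calls for 45 mg. Between 3.84 and 4.64 she passes exclusion 6 when she should not.

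**Step 3: a smaller adolescent.** Boy of 13, 45 kg, 155 cm, assumed above the 5th weight percentile.
- BSA = √(45 × 155 / 3600) = 1.392.
- CG = 127 × 45 / (72 × Scr) = 79.38/Scr; indexed = 98.65/Scr.
- Reduction at 55: unindexed above 79.38/55 = 1.44 mg/dL; indexed above 98.65/55 = 1.79.

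Between 1.44 and 1.79 mg/dL he is cut from 45 to 30 mg while above the tabled threshold.

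**Step 4: are the tabled values the intended thresholds?** They can be compared with 30% and 50% of (mean − SD), using the appendix's own means and SDs.

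| Row | Mean − SD | 30% | Tabled | 50% | Tabled |
|---|---|---|---|---|---|
| 1 week | 26 | 7.8 | 10 | 13 | 15 |
| 2-8 weeks | 41 | 12.3 | 10 | 20.5 | 20 |
| >8 weeks | 74 | 22.2 | 20 | 37 | 35 |
| 2-12 years | 106 | 31.8 | 30 | 53 | 50 |
| 13-21 years, male | 110 | 33 | 35 | 55 | 55 |
| 13-21 years, female | 104 | 31.2 | 30 | 52 | 50 |

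Rounded to the nearest 5, 11 of 12 match; the exception is 53, tabled as 50. The values look deliberate, so they are the right yardstick for Steps 1 to 3.

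**The case against.** **The sponsor may have meant absolute clearance.** Section 1.1 states the US adult labelling limit as a creatinine clearance in mL/min. Adolescents receive fixed tablets by weight band, aimed at adult 60 mg exposure. On that reading the column unit is wrong for this cohort and no BSA step is missing. This stands as a possibility, and the fix has to allow for it. It does not rescue the page, because indexed values would still be serving as absolute cut-offs. The criterion's wording, relative to normal for the child's age and size, favours indexing without settling the matter.

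**Sites, the laboratory or the IXRS may convert.** Their specifications are not in the documents. A reader might infer that adolescents were in fact wrongly enrolled or dosed. The documents support only what happens if the text is followed.

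**Few subjects would change category.** This stands. Subjects near 1.73 m² are unaffected, and only those close to a cut-off move. Those below the "5th Percentile for Age" already receive 30 mg with no further reduction, so their dose cannot change. Exclusion 11 also lets the investigator keep out a subject judged at increased risk, so enrolment at a high creatinine does not rest on the table alone.

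**The cut-offs themselves might look wrong.** For males aged 13 and over, 35/140 is 25% and 55/140 is 39% of the listed mean. A reader might infer that the thresholds should be higher. Step 4 of the working argues against that, and footnotes a and b make the tabled values the ones to apply. At most, the Mean eGFR label on the two cut-off columns is a poor description.

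**Conclusion.** Wrong as written for ages 12 to <18. The formula and the cut-offs are in different units, and nothing in the Synopsis, Sections 4.2, 5.1.1.1.1, 5.1.2, 5.3.1, 5.6.3 and 9.8.3 or Appendix 17.7 reconciles them. Followed literally, the effective threshold is about a third too high at BSA 1.3 m² (factor 1.33) and about 18% too low at 2.1 m² (factor 0.82), relative to the tabled indexed values. Errors run in both directions; the one towards over-exposure falls on large adolescents.

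Confidence is high in the inconsistency. The sizes rest on assumed BSA and body measurements, and the direction rests on the tabled indexed values being the intended thresholds. The number affected cannot be derived, because no rate of renal impairment is given. A reader might also infer a bias in the primary non-inferiority comparison. Nothing in the documents shows one: eligibility is settled before randomization, and the dose effect is limited to a probably small group in one arm.

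**What to change.** For ages 12 and over, add one line to Appendix 17.7: multiply the Cockcroft-Gault result by 1.73/BSA, with a named BSA formula, before comparing it with the table. Height and weight are already collected with the physical examination (Section 9.10, Table 17.1). If the sponsor intends absolute clearance for this cohort, restate the cut-offs for ages 12 and over in mL/min instead.

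In either case, state that the tabled values are the operative thresholds for exclusion 6 and for dose reduction. Correcting the Mean eGFR label is optional.

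The cost is an amendment to one appendix, a notice to sites, and a check of how eGFR is computed at screening and for the IXRS dose-reduction entry. The oldest cohort enrols first (Section 3.2), and its data have already had IDMC review. Adolescents already enrolled or dosed therefore need a retrospective check from recorded height, weight and creatinine, and the prospective gain is smaller than it would have been at the start. No new data, design change or sample-size change is needed.
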